10. APPENDICES

Appendix 1. DATA DERIVATION DETAILS

Endpoint	Derivation
24-hour seizure rate at baseline (b) phase (Count/24 hours)	$24\text{-hour seizure rate}_b = [(\# \text{ of seizures}_b) \div (\# \text{ of hours}_b \text{ of Video- EEG monitoring})] \times 24$
24-hour seizure rate at double-blind treatment (t) phase (Count/24 hours)	$24\text{-hour seizure rate}_t = [(\# \text{ of seizures}_t) \div (\# \text{ of hours}_t \text{ of Video- EEG monitoring})] \times 24$
Primary endpoint: Log _e of 24-hour seizure rate at double-blind treatment phase	$\text{Log}_e (24\text{-hour seizure rate}_t + 1)$
Log transformed baseline 24-hour seizure rate	$\text{Log}_e (24\text{-hour seizure rate} + 1)$ at baseline
“Percent reduction in seizures” relative to placebo	
Example: A difference between one of the pregabalin doses and placebo of -0.400 on the log transformed scale for the 24-hour seizure rate translates into a 33% reduction in the 24-hour seizure rate of the pregabalin group from the placebo group (ie, $100\% \times [\exp^{-0.400} - 1] = -33\%$)
 
An additional back transformation will be calculated for the percent reduction in seizures for each pregabalin treatment group relative to placebo for presentation in the CSR as follows:
 $100\% \times \frac{[\exp(\text{LSMean(pregabalin)}) - 1] - [\exp(\text{LSMean(placebo)}) - 1]}{\exp(\text{LSMean(placebo)}) - 1}$
Change from baseline in 24-hour seizure rate	$\text{Change} = 24\text{-hour seizure rate}_t - 24\text{-hour seizure rate}_b$
Percent change from baseline in 24-hour seizure rate for calculation of responders	$\% \text{ Change} = [24\text{-hour seizure rate}_t - 24\text{-hour seizure rate}_b] / 24\text{-hour seizure rate}_b \times 100$
Responders	$\geq 50\%$ reduction in the 24-hour seizure rate from baseline during the double-blind 48 hour Video EEG period, then response = 1 (responder) otherwise response = 0 (non-responder)

Appendix 2. STATISTICAL METHODOLOGY DETAILS

Appendix 2.1. Further Details of Interim Analyses

Appendix 2.1.1. Blinded Sample Size Re-estimation

The sample size re-estimation formula of Friede and Keiser (2011)¹ for this study is the following:

$$N = \frac{(1+\gamma)^2}{\gamma} (z_{1-\alpha/2} + z_{1-\beta})^2 \frac{(1-\rho^2)\sigma_Y^2}{(\Delta^*)^2}$$

where,

$N = N_A + N_B$, $N_B = \gamma^* N_A$ and z_p is the p -quantile of the standard normal distribution; $z_{1-\alpha/2}$ is a percentile from a standard normal cdf with $\alpha/2=0.025$; $\gamma=1$ assumes equal sample sizes; for this study the two groups are placebo and 7 mg/kg/day which are in 1:1 ratio.

$z_{1-\beta}$ is a percentile from a standard normal cdf with $\beta=0.20$;

ρ = correlation between primary endpoint and baseline;

$$\sigma^2 = (1 - \rho^2)\sigma_Y^2$$

\tilde{s}^2 is the unbiased estimate of σ^2 , which can be shown to equal the residual variance.

$\Delta = -0.355$ is the planned difference (ie, 7 mg/kg/day and placebo) for the sample size re-estimation. The details for deriving this delta are in the SSRE plan.

The Guenther adjustment for equal sample sizes per group, leads to the final computation:

$$N_G = N + \frac{(z_{1-\alpha/2})^2}{2}$$

$n^* = N_G/2$; where n^* is the number of subjects per group (rounded to the nearest integer) for Pregabalin 7 mg/kg/day and placebo. Since the randomization ratio for this study is 2:2:1 for (Placebo: pregabalin 7 mg/kg/day: pregabalin 14 mg/kg/day), the number of subjects for pregabalin 14 mg/kg/day will be $n^*/2$, and $2.5 \times n^*$ is the total subjects.

The pooled blinded estimate of the variance, \tilde{s}^2 , will be based in a blinded manner without making any correction for possible treatment group differences after the 1st approximately 2/3 of the planned 123 subjects have had the opportunity to complete the study. Since baseline 24-hour seizure rate, age strata, and geographical region are important pre-specified modeling terms that explain sources of variability in the data, the estimate \tilde{s}^2 will take into consideration these three modeling terms as the mean squared error. While this pooled estimate of the variance under the null hypothesis will be biased upwards, this bias is negligible when the overall sample is reasonably large. The proposed blinded sample size re-estimation procedure will only allow for a new sample size (n_{New}) to be increased beyond

the initial targeted sample size (n_{Initial}). The n_{New} is estimated to keep at least the power of 0.8 for comparison of between Dose Level 1 and Placebo when estimated SD is larger than initial SD. In addition, the n_{New} is also estimated to keep the randomization ratio of Placebo, Dose Level 1, Dose Level 2 in 2:2:1. The proposed blinded sample size re-estimation procedure will only allow for a new sample size (n_{New}) to be increased beyond the initial targeted sample size (n_{Initial}), but not beyond the pre-determined maximum sample size ($n_{\text{Max}}=150$).

Appendix 2.2. Further Details of the Statistical Methods

Appendix 2.2.1. Analysis Strategy Using Multiple Imputations

Multiple imputation procedure is used under the assumption of missing at random (MAR) data. The goal of the imputation strategy is to produce a completed dataset. This dataset has two time points, baseline and on study. The pattern of missing data is implicitly, monotone. It is likely that little or no data is missing at baseline. In general, let \mathbf{Y} be the response data $[\log(\text{double blind 24-hour EEG seizure rate} + 1)]$ where that part of \mathbf{Y} which is missing is denoted by \mathbf{Y}_{mis} , and that part of \mathbf{Y} which is observed is denoted by \mathbf{Y}_{obs} . A data pattern is said to have a missing monotone data pattern when the variable \mathbf{Y}_j for an individual subject is missing at time point j , and all subsequent variables for that individual are also missing for \mathbf{Y}_k in which $k > j$. In this data there are only two assessment time points, baseline and the on-study measurement.

The three steps for conducting statistical inferences using a multiple imputation procedure consist of the following:

Imputation step: Missing data are filled in m times to generate m complete data sets, where $m > 1$; for this study, m will take on the value 5.

Analysis step: The m complete data sets are analyzed using standard procedures.

Combination step: The results from the m complete data sets are combined for the final statistical inference.

The imputation step is perhaps the most critical, since it relies upon assumptions regarding the missing data mechanism. The goal of the imputation is to account for the relationships between the unobserved and observed variables, while taking into account the uncertainty of the imputation. The MAR assumption is key to the validity of multiple imputations. Use of this assumption allows the analyst to generate imputations $(\mathbf{Y}_{\{1\}}, \mathbf{Y}_{\{2\}}, \dots, \mathbf{Y}_{\{m\}})$ from the distribution $f(\mathbf{Y}_{\text{mis}} | \mathbf{Y}_{\text{obs}})$, since after conditioning on \mathbf{Y}_{obs} , the missingness is assumed to be due to chance and is considered ignorable. In this application, we will use the regression method in which the variable \mathbf{Y}_j with missing values is fitted with non-missing observations as the dependent variables. This allows for the following regression model to be employed:

$$\mathbf{Y}_0 = \beta_0 \text{ and } \mathbf{Y}_1 = \beta_0 + \beta_1 * \mathbf{Y}_1.$$

The fitted model has parameter estimates (β_0, β_1) and the associated covariance matrix $s_j^2 V_j$, where V_j is the usual $\mathbf{X}^T \mathbf{X}$ matrix from the intercept and variable \mathbf{Y}_1 .

For each imputation, new parameters (β_0^* , β_1^* ; and σ^{*2}) are drawn from a posterior predictive distribution of the missing data. The missing values of Y_j are then replaced with the predicted values using the following equation:

$$\beta_0^* + \beta_1^* * y_1 + z_i * \sigma^{*2}$$

where y_1 is the covariate value for the first variable and z_i a simulated standard normal deviate for the i^{th} individual.

The next step is to carry out the analysis of interest for each of the m imputed complete-observation datasets, storing the parameter vector and standard error estimates.

Finally, the results are combined using results from Rubin (1987) to calculate estimates of the within imputation and between imputation variability. These statistics account for the variability of the imputations and assuming that the imputation model is correct, provide consistent estimates of the parameters and their standard errors. The imputation model need not be exactly correct and the MI will provide these consistent estimates. The following are additional information and suggested code that can be used for MI:

In this appendix, we will assume that data are stored in a SAS dataset, with the following variables. Note that the variable names/labels are suggestions only and the actual names/labels and code levels should be consistent with current sponsor reporting standards.

SUBJID: subject identification number.

REGION and AGE_STRATA.

TRT: Treatment group (Placebo, Pregabalin 7.0 mg/kg/day, Pregabalin 14.0 mg/kg/day).

LN_BSZRT: A \log_e transformed baseline seizure rate $\log_e(\text{Baseline 24-hour seizure rate}_b + 1)$.

LN_SZRATE: A \log_e transformed double-blind seizure rate $\log_e(\text{Double blind 24-hour seizure rate}_t + 1)$.

IMPSTAT: Impstat = 1 if DC due to AE, death, or insufficient clinical response.
Impstat = 2 otherwise.

MISS: Miss = 1 if ln_szrate is missing. Miss = 0 otherwise.

In order to impute missing data at the singular time point and based on the definition of the link function, first prepare an input dataset, making sure that it will contain only the intended donor and recipient patterns. Separate the input dataset <efficacy> into two datasets: IMP, containing all placebo subjects and those subjects from the pregabalin arms that have missing LN_SZRATE [Miss=1] and Impstat=1; and REST, containing the rest of the subjects from the pregabalin arms (those with non-missing LN_SZRATE [Miss=0] or Impstat=2).

title1 'Pattern Imputation based on reason for DC';

*these sets are exhaustive and mutually exclusive;

```
data IMP REST;
  set <efficacy>;
  if trt ne "Placebo" and (impstat = 2 or miss = 0) then output REST;
  if trt = "Placebo" or (impstat = 1 and miss = 1) then output IMP;
run;
```

Call PROC MI to impute missing data at the time point using dataset IMP as input.

*order of variables matters in proc mi;

```
proc mi data = IMP out = impout nimpute=100 seed = 233;
  class region age_strata;
  var region age_strata ln_bszrt ln_szrate;
  monotone regression(ln_szrate = ln_bszrt region age_strata);
run;
```

Call PROC MI to impute missing data at the time point using dataset REST as input.

*impute like randomized trt for active who are 'ignorably missing';

```
proc mi data = REST out = restout nimpute=100 seed = 238 ;
  class region age_strata trt ;
  var region age_strata trt ln_bszrt ln_szrate ;
  monotone regression(ln_szrate = trt ln_bszrt region age_strata) ;
run;
```

Assemble back a dataset containing all subjects.

*fully imputed integrated dataset;

```
data main ;
  set impout restout ;
run ;
proc sort data = main ;
  by _imputation_ trt ;
run ;
```

*Analysis of imputed data sets;

* Confirm the ordering of the trt variable for specifying the vector. Here it is assumed Placebo, Pregabalin 7.0 mg/kg/day, and Pregabalin 14.0 mg/kg/day ;

```
proc glm data=main;
  by _imputation_ ;
  class region age_strata trt ;
  model ln_szrate = trt region age_strata ln_bszrt ;
  lsmeans trt / diff=control('Placebo') tdiff pdiff cl;
  estimate 'Pregabalin 7.0 mg/kg/day vs Placebo' trt -1 1 0 ;
  estimate 'Pregabalin 14.0 mg/kg/day vs Placebo' trt -1 0 1 ;
  ods output lsmeans=lsm diffs=lsdiff estimates=estdiffs ;
run ;
```

quit ;

*integrated summary of results of imputed datasets, please note the degree of freedom (XXX) should come from MSE of GLM model above;

```
proc mianalyze parms(classvar=full)=lsm edf=XXX;
  class trt ;
  modeleffects trt ;
run ;
proc sort data = estdiffs ;
  by parameter _imputation_ ;
run ;
proc mianalyze data=estdiffs edf=XXX;
  by parameter ;
  modeleffects estimate ;
  stderr stderr ;
run ;
```

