In order to address the primary analysis comparison between placebo and the Level 1 dose group, a sample size of 44 in each of these two groups will provide at least 80% power to detect a true difference of -0.448 using a two-sided test at the 0.05 level of significance with a standard deviation of 0.73.

Randomization will be stratified by subject age (Stratum 1: <1 year of age; Stratum 2: 1-2 years of age; Stratum 3: >2 years of age). Subjects in each age stratum within the site will be randomized to either placebo or 1 of 2 fixed doses of pregabalin divided TID, Dose Level 1: pregabalin 7 mg/kg/day [6 mg/kg/day for subjects 1 to 3 months of age] or Dose Level 2: pregabalin 14 mg/kg/day [12 mg/kg/day for subjects 1 to 3 months of age] in a 2:2:1 ratio. Every reasonable effort will be made to enroll a minimum of 10 subjects in each of the 3 age strata.

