6. ENDPOINTS AND COVARIATES

6.1. Efficacy Endpoint(s)

6.1.1. Primary Efficacy Endpoint

- *The primary endpoint will be the log transformed double blind 24 hr seizure rate for all partial onset seizures collected at Visit 6 (48 hour Video-EEG assessment phase) during the double blind phase as determined by the central reader. This 24-hour seizure rate will be calculated as follows for the double-blind period:*

$$\text{Double Blind 24 - hr EEG seizure rate} = \frac{\text{\# of seizures in double blind 48 - hr assessment phase}}{\text{\# of hours of Video - EEG monitoring}} \times 24$$

- When the log-transformation is used, the quantity 1 is added to the double blind 24-hr EEG seizure rate for all subjects to account for any possible "0" seizure incidence. This will result in the following primary efficacy measure: $\log_e(\text{double blind 24-hr EEG seizure rate} + 1)$. Results will be reported as "percent change in seizures" relative to placebo. For example, a difference between one of the pregabalin doses and placebo of -0.400 on the log transformed scale for the double blind 24-hr seizure rate, translates into a 33% reduction in the double blind 24-hour EEG seizure rate of the pregabalin group from the placebo group (ie, $100\% * [\exp^{-0.400} - 1] = -33\%$).
- An additional back transformation will be calculated for percent reduction in seizures for each pregabalin treatment group relative to placebo for presentation in the CSR as follows: $100\% \times \frac{[\exp(\text{LSMean(pregabalin)}) - 1] - [\exp(\text{LSMean(placebo)}) - 1]}{\exp(\text{LSMean(placebo)}) - 1}$
- A minimum of 24 hours of evaluable Video-EEG will be required to utilize the EEG. In cases where there is less than 24 hours of evaluable Video-EEG, the seizure rate will be set to missing.
- The baseline 24-hr EEG seizure rate will be calculated in the same respective manner.

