8.1. Statistical Methods

8.1.1. Analyses for Continuous Data

ANCOVA methods will use a linear model with treatment, age stratum, and geographical region (as defined in *Table 2* above) as fixed factor effects, and baseline as a continuous covariate. This linear model will include both dose groups of pregabalin.

- Least square means will be calculated using the observed marginal distribution. Two-sided 95% confidence intervals of the difference between the least square means will be calculated by using the appropriate least square means and their standard errors.

Sensitivity analyses will include non-parametric analyses including analysis of covariance based on the rank transformed data, and a Wilcoxon-Mann Whitney test; and handling of missing data using multiple imputation methods (See [Appendix 2.2.1](#)).

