8.2. Statistical Analyses

8.2.1. Analysis of Primary Endpoints

The primary analysis will be performed on the primary endpoint, \log_e (double blind 24-hour EEG seizure rate +1), using a linear model with treatment, age stratum, and geographical region (as defined in Table 2 above) as fixed factor effects, and \log_e (baseline 24-hour EEG seizure rate +1) as a continuous covariate. This linear model will include both dose groups of pregabalin. This analysis will be applied for all subjects who satisfy mITT criteria and for data of observed case.

Each dose of pregabalin and placebo will be compared using a sequential step-wise testing procedure. For this analysis, the following steps will be applied:

- *Step 1: Test the difference between the Level 2 group and placebo.*
 - $H_{01}: \mu_{\text{Level 2}} - \mu_{\text{Placebo}} = 0$
 - $H_{a1}: \mu_{\text{Level 2}} - \mu_{\text{Placebo}} \neq 0$
- *Step 2: Test the difference between the Level 1 group and placebo.*
 - $H_{02}: \mu_{\text{Level 1}} - \mu_{\text{Placebo}} = 0$
 - $H_{a2}: \mu_{\text{Level 1}} - \mu_{\text{Placebo}} \neq 0$

If H_{01} is rejected ($p \leq 0.05$) then move to step 2, otherwise claim no difference and stop. If H_{02} is rejected ($p \leq 0.05$) then claim a difference for all the comparisons, otherwise claim differences between 14 mg/kg/day and placebo only.

Least square means will be calculated using the observed marginal distribution. Two-sided 95% confidence intervals of the difference between the least square means will be calculated by using the appropriate least square means and their standard errors. Results will be reported as “percent reduction in seizures” relative to placebo. For example, a difference between one of the pregabalin doses and placebo of -0.400 on the log transformed scale for the 24-hour seizure rate, translates into a 33% reduction in the 24-hour seizure rate of the pregabalin group from the placebo group (ie, $100\% \times [\exp^{-0.400} - 1] = -33\%$).

An additional back transformation will be calculated for percent reduction in seizures for each pregabalin treatment group relative to placebo for presentation in the CSR as

$$\text{follows: } 100\% \times \frac{[\exp(\text{LSMean(pregabalin)}) - 1] - [\exp(\text{LSMean(placebo)}) - 1]}{\exp(\text{LSMean(placebo)}) - 1}$$

Sensitivity Analysis

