The same analysis as the primary, except for missing data imputation and analysis set, will be performed as a sensitivity analysis. In this analysis, a multiple imputation technique for missing data will be applied for the ITT population. This sensitivity analysis will only be applied for the ITT analysis set, and all other efficacy analyses will be applied for the mITT analysis set.

A non-parametric analysis of covariance based on the rank transformed data will be performed and evaluated for efficacy results in combination with the primary analysis.

A Wilcoxon-Mann Whitney test will also be performed and reported for the primary endpoint.

Other Supplemental Analyses

The primary analysis of the primary endpoint will be evaluated for violations to model assumptions based on descriptive statistics, box plots and residual plots.

The change from baseline in 24-hour seizure rate, with and without log-transformation, will be analyzed descriptively for each treatment group using tables and plots.

A generalized linear model assuming a Poisson distribution and canonical log link function will be applied to the raw seizure counts (McCullagh and Nelder, 1989 and Stokes et al., 2000).^{2,3} The model will have an off-set parameter for the amount of evaluable time (ie, $\log_e(\text{time monitored})$) the subject was with V-EEG. Over-dispersion will be investigated, and if it appears to exist for this model, then the scale parameter will be set to the deviance in the Poisson model, and a negative binomial will be also be explored in addition to analyzing the data with a quasi-likelihood function. This analysis will assume missing completely at random, and will assess seizure frequency in relation to the amount of time each subject was at risk relative to their evaluable hours of V-EEG monitoring. In addition, this analysis will not be subject to any potential extrapolation of applying the 24 hour seizure rate. Further details will be provided in Appendix 2.2.2.

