8.2.4. Summary of Efficacy Analyses

Endpoint	Analysis Set	Statistical Method	Model/ Covariates/ Strata	Output	Missing Data	Interpretation
Log _e (24-hour seizure rate +1) (DB Phase)	mITT	ANCOVA	Treatment, age strata, region and log-BL log-BL = Log _e (24-hour seizure rate +1) at baseline	Log-Scale - LS mean and 95% CI by treatment group, - LS mean difference from placebo, SE, 95% CI and p-value Original (Back Transformed) - LS Mean and 95% CI by treatment group - “Percent Change in Seizures” Relative to Placebo	OC	Primary Analysis
Log _e (24-hour seizure rate +1) (DB Phase)	ITT	ANCOVA	Treatment, age strata, region and log-BL	Log-Scale - LS mean and 95% CI by treatment group, - LS mean difference from placebo, SE, 95% CI and p-value Original (Back Transformed) - LS Mean and 95% CI by treatment group - “Percent Change in Seizures” Relative to Placebo	MI	Sensitivity Analysis
Log _e (24-hour seizure rate +1) (DB Phase)	mITT	Rank ANCOVA	Treatment, age strata, region and ranked log-BL	Log-Scale - Median by treatment group - LS mean difference from placebo, SE, 95% CI and p-value	OC	Sensitivity Analysis
Log _e (24-hour seizure rate +1) (DB Phase)	mITT	Wilcoxon-Mann Whitney Test		Log-Scale N, Mean, SD, Median, Min, Max, 25%, 75%, Test Statistics and p-value	OC	Sensitivity Analysis
Log _e (24-hour seizure rate +1)	mITT	Descriptive		N, Mean, SD, Median, Min,	OC	Evaluation for

Endpoint	Analysis Set	Statistical Method	Model/ Covariates/ Strata	Output	Missing Data	Interpretation
(BL, DB and Chg. from BL)		Statistics		Max, 25%, 75%, Skewness and Kurtosis		violations to model assumption
Log _e (24-hour seizure rate +1) (BL, DB and Chg. from BL)	mITT	Plot		Box Plot and Histogram of endpoint by Treatment Group	OC	Evaluation for violations to model assumption
Log _e (24-hour seizure rate +1) (DB Phase)	mITT	ANCOVA (Plot)	Treatment, age strata, region and log-BL	Residual Plot of Primary Analysis	OC	Evaluation for violations to model assumption
Responder Rate	mITT	Logistic Regression	Treatment, age strata, and region	Odds Ratio, 95% CI and p-value	OC	Secondary Endpoint
Responder Rate	mITT	Descriptive Statistics		N ¹ , n ² and %	OC	Secondary Endpoint
Raw Seizure Count	mITT	GLM	Assumption of a Poisson distribution and canonical log link function	Goodness of Fit, maximum likelihood estimates, least squares means, and p-values	OC	Supplemental Analysis

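### The suggested multiple-imputation code does not request observed-margin LS means, so the back-transformed rates by arm in the imputation row would generally not be on the same weighting as the primary analysis

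*SAP*

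**What the plan says.** On LS means, SAP 8.1.1 states: "Least square means will be calculated using the observed marginal distribution". SAP 8.2.1 repeats this for the primary analysis, and protocol 9.2.1 says the same.

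On the imputation analysis, SAP 8.2.1 states: "The same analysis as the primary, except for missing data imputation and analysis set, will be performed as a sensitivity analysis". Weighting of LS means is not among the exceptions.

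Appendix 2.2.1 supplies suggested code. Its analysis model is "model ln_szrate = trt region age_strata ln_bszrt", which is additive with no interaction. Its LS-means statement is "lsmeans trt / diff=control('Placebo') tdiff pdiff cl". The LS means from that statement are the ones passed to the pooling step. The pooled treatment differences come separately, from ESTIMATE statements.

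Two percent figures are defined. The first depends only on the log difference; in the worked example, -0.400 "translates into a 33% reduction in the 24-hour seizure rate of the pregabalin group from the placebo group". The second is introduced in SAP 6.1.1: "An additional back transformation will be calculated for percent reduction in seizures for each pregabalin treatment group relative to placebo". It subtracts 1 from each exponentiated LS mean and divides by exp(LSMean placebo) - 1.

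The table in SAP 8.2.4 lists "LS mean and 95% CI by treatment group" on the log scale for both the primary and the imputation rows. For both rows it also asks for the back-transformed LS means with intervals, and for a percent change relative to placebo.

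**The concern.** The imputation row exists to show whether missing follow-up recordings change the answer. For that, it should differ from the primary row only in the imputation and the analysis set. If the LS means are also averaged over regions and age strata with different weights, the two rows' seizure rates by arm are not like for like, and part of any gap reflects the weighting.

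Equal weights would match the observed mix only by chance. For age, the plan says only: "Every reasonable effort will be made to enroll a minimum of 10 subjects in each of the 3 age strata". The three pooled regions in SAP Table 2 contain 6, 2 and 14 countries.

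The additional percent figure makes the level of the LS means matter as well as their difference. According to the SAP's amendment table, the imputation code was added in Amendment 3 (March 2018) and this figure in Amendment 4 (April 2018), so the code predates the figure that is sensitive to the weighting.

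**Working it through.** **Inputs.** From the documents: the additive model and LS-means statement (SAP Appendix 2.2.1), the two percent formulas (SAP 6.1.1 and 8.2.1), and the planned difference d = -0.355 for Level 1 on the +1 scale (SAP Appendix 2.1.1). Assumed: region and age shares, factor effects, the placebo LS mean, and equal class-level weights as the default of the LS-means statement.

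**1. The plan's own example.** 100 × [exp(-0.400) - 1] = -32.97%, which reproduces the stated -33%.

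**2. What the margin choice changes.** In an additive model each arm's LS mean is the treatment effect, plus weighted averages of the region and age effects, plus the baseline term. Changing the weights adds the same constant s to every arm. Therefore:

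- The log differences, their standard errors, intervals and p-values, and exp(d) - 1, are unchanged.
- Each back-transformed rate, exp(L) - 1, changes, as does its interval.
- The additional figure equals 100 × [exp(d) - 1] × exp(L) / [exp(L) - 1], where L is the placebo LS mean, so it changes with L.

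**3. Size under one assumed imbalance.** One region holds 10% of children and has a mean log rate 0.5 to 0.8 below the other two, which are alike; age adds nothing. Equal weighting raises that region's weight from 0.10 to 1/3, so LS means fall by gap × (1/3 - 0.10):

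- gap 0.5: 0.117
- gap 0.8: 0.187

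With d = -0.355, exp(d) - 1 = -29.9% throughout.

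| Placebo LS mean at observed margins | Gap | LS mean used | Placebo rate per 24 h | Additional figure |
|---|---|---|---|---|
| 1.3 | none | 1.300 | 2.67 | -41.1% |
| 1.3 | 0.5 | 1.183 | 2.26 | -43.1% |
| 1.3 | 0.8 | 1.113 | 2.04 | -44.5% |
| 1.7 | none | 1.700 | 4.47 | -36.6% |
| 1.7 | 0.5 | 1.583 | 3.87 | -37.6% |
| 1.7 | 0.8 | 1.513 | 3.54 | -38.3% |

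The additional figure moves by 1.0 to 3.4 points.

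**4. Check by fitting the model.** The additive ANCOVA was fitted to simulated complete data (150 subjects, 60:60:30, nothing missing), with LS means taken both ways.

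- Moderate imbalance (age 30/52/68, region 60/22/68, assumed effects): placebo LS mean 1.357 at observed and 1.462 at equal margins; placebo rate 2.89 and 3.31. The additional figure is -46.6% and -45.0% for Level 2, and -27.5% and -26.6% for Level 1. The log differences (-0.4246 and -0.2286) and the first percent figure (-34.6% and -20.4%) are identical under both.
- Strong imbalance (age 10/50/90, region 90/15/45): placebo rate 3.34 and 4.04; Level 2 additional figure -60.5% and -58.0%.
- Exactly balanced factors (50/50/50 each): no difference.

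Here the shift is upward and in step 3 it is downward. The direction depends on whether the small groups have higher or lower rates.

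**5. Sensitivity to the placebo level.** With d = -0.355 and an assumed upward shift of 0.1 to 0.3, the additional figure moves from -34.6% to between -34.1% and -33.2% at LS mean 2.0. At LS mean 0.8 it moves from -54.3% to between -50.4% and -44.8%. Large movements need both a low placebo rate and a large shift.

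**The case against.** The best defence is that the text already governs. Appendix 2.2.1 offers the code as a suggestion and leaves placeholders in it, and SAP 8.2.1 already carries the observed-margin rule over to the imputation analysis. A programmer who follows the text would add the option. This stands, and it is why the point is conditional on the code being run unchanged. But the amendment table says the code was added to help programming, so it is likely to be copied.

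Three stronger readings are tempting, and the documents do not support them.

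- **That the efficacy conclusion or the type I error is at risk.** It is not. The model is additive, the pooled differences come from ESTIMATE statements that do not use margins, and the step-wise tests belong to the primary analysis.
- **That nothing in the output could reveal the shift.** The same row prints the log difference, its interval and p-value, none of which depends on the margins. A reader can judge the effect of missing data from these. Only the level-dependent quantities beside them are affected.
- **That the plan expressly requires the additional percent figure for the imputation row.** The 8.2.4 table does not say which percent formula it means, and 8.2.1 presents the additional formula before the sensitivity analyses. Its use there is an inference from the rule that the two analyses are otherwise the same. The back-transformed LS means by arm are expressly listed.

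The assumed gap of 0.5 to 0.8 is also large. It exceeds the planned effect of 0.355 and is 0.7 to 1.1 times the design SD of 0.73 (which is on the old +1/28 scale). The amendment table says regions were re-pooled so that each would have an adequate number per treatment, which works against a very small region. The figures are therefore illustrations.

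**Conclusion.** The mismatch between text and code is real and minor. Run as printed, and assuming equal weights are the default, the code would give back-transformed LS means by arm that generally differ from the primary analysis for reasons unrelated to missing data. The additional percent-reduction figure would differ as well if it is reported for that row. The gap vanishes only if regions and age strata are exactly balanced or their estimated effects cancel, and the design enforces neither.

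The size cannot be fixed from the documents, which give no region or stratum counts, factor effects or placebo level. The assumed regional imbalance gives about 1 to 3.4 points on the additional figure, and the two imbalanced simulations give about 1 to 2.5 points. The comparison also assumes that the primary analysis, whose code is not shown, follows the text. This is a consistency defect in the reporting of one sensitivity analysis.

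**What to change.** In Appendix 2.2.1, add the observed-margins option to the LS-means statement. In SAP 8.2.1, state that the back-transformed LS means and the additional percent-reduction figure use observed-margin LS means in both the primary and the imputation analyses, and say whether the additional figure is to be reported for the imputation row. The exp(difference) - 1 figure needs no such statement.

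Also name the data set that supplies the margins. Under SAP 5.4.1 the ITT set adds children without a follow-up recording, so its region and age mix and its mean baseline can differ from those of the mITT set even with the option in place. Either use the same reference margins for both rows, or use the ITT margins for the imputation row and note the difference.

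The cost is one option in the code and two or three sentences, with no effect on the design, the tests or data collection.
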